2. SYNOPSIS

Study Title	An observational study to correlate the results of ploidy and stroma analysis with prognosis in early rectal cancer	
Internal ref. no. (or short title)	Ploidy and stroma in early rectal cancer	
Study Design	Observational study	
Study Participants	Rectal cancer patients	
Planned Sample Size	150 patients	
Follow up duration	Minimum 18 months	
Planned Study Period	2 years	
	Objectives	Outcome Measures
Primary	To compare results of [A] ploidy and [B] stroma analysis with outcome after surgery to remove early rectal cancer	Correlation between [A] ploidy status and [B] tumour: stroma ratio with local recurrence of cancer
Secondary	
To compare results of [A] ploidy and [B] stroma analysis with survival after surgery to remove early rectal cancer
 
To assess predictive value of [A] ploidy and [B] stroma analysis for outcome after surgery to remove early rectal cancer
 
To compare results of [A] ploidy and [B] stroma analysis with outcomes by use of adjuvant treatment
	
Correlation between [A] ploidy and [B] stroma analysis with overall survival after TEM surgery to remove rectal cancer
 
Contribution of [A] ploidy and [B] stroma analysis to a regression model for local recurrence after TEM surgery to remove rectal cancer
 
Subgroup analysis comparing [A] ploidy and [B] stroma results with local recurrence and survival for patients who did and did not receive adjuvant chemo- or radiotherapy

3. ABBREVIATIONS

CAG	Confidentiality Advisory Group
CI	Chief Investigator
CRA	Clinical Research Associate (Monitor)
CRF	Case Report Form
CRO	Contract Research Organisation
GCP	Good Clinical Practice
GP	General Practitioner
ICF	Informed Consent Form
ICH	International Conference on Harmonisation
IRB	Independent Review Board

MRN	Medical Records Number
NHS	National Health Service
NRES	National Research Ethics Service
PI	Principal Investigator
PIS	Patient Information Sheet
R&D	NHS Trust R&D Department
REC	Research Ethics Committee
SDV	Source Data Verification
SOP	Standard Operating Procedure
TEM	Transanal endoscopic microsurgery
TMF	Trial Master File

4. BACKGROUND AND RATIONALE

Early rectal cancer can be removed by minimally-invasive surgery, and the standard pathological assessment of the removed tumour gives valuable information about how advanced the tumour is. This information is very important in indicating whether the cancer is likely to recur, and therefore in advising the patient after surgery whether further treatment is advisable, and if not, what is the most appropriate follow-up regime. However there is still a lot of uncertainty in these predictions about recurrence of the cancer, and better tests are being sought. This study aims to look at two further pathology tests, ploidy and stroma ratio in the tumour, and compare these test results with outcome in patients who have had an early rectal cancer removed. This will allow us to assess whether these two tests can give greater accuracy in predicting outcome. If so, we would be better able to advise patients with early rectal cancer about their prognosis and further management.

Routine histopathology analysis of a rectal cancer specimen removed at surgery includes assessment of tumour size, depth of invasion, vascular, lymphatic and perineural invasion, tumour involvement of resection margins and nodal involvement. This information is valuable in predicting outcome. For example, predicted rates of local recurrence at 36 months following local excision of rectal cancer by transanal endoscopic microsurgery (TEM) based on tumour size, depth of invasion and lymphatic invasion have been tabulated [1]. However such models are not perfect, and leave room for improvement. Ploidy and stroma ratio are two further tests which have shown some promise in predicting outcome.

Ploidy refers to the number of sets of chromosomes in a cell nucleus. Most human cells are normally diploid, with two sets of 23 chromosomes. Abnormal tumour cells may have a different number of sets of chromosomes, or be aneuploid, having some replicated or deleted chromosomes. In general, aneuploidy in cancer cells is associated with a worse prognosis. An early study of DNA ploidy in rectal cancer using flow cytometry showed an independent but small predictive effect of aneuploidy on survival [2]. Technological advances now allow more accurate and detailed assessment of ploidy. The DNA ploidy status of tumour cells in early ovarian cancer has been found to predict which patients will

benefit from adjuvant chemotherapy after surgery to remove the ovarian tumour and is used routinely in some centres to aid in decision-making [3].

Stroma ratio refers to the tumour: stroma ratio. A lower proportion of tumour cells or, conversely, a higher percentage of stroma, in a cancer tends to be associated with a poorer prognosis. This ratio has been found to be strongly associated with tumour growth and invasion in colorectal cancers, and to independently predict survival in patients undergoing surgery to remove colorectal tumours [4]. However previous studies have looked mainly at more advanced colon cancers, rather than early rectal cancers, and have used only cancer-related death as the endpoint, rather than looking at local recurrence and response to adjuvant treatments.

5. OBJECTIVES AND OUTCOME MEASURES

Objectives	Outcome Measures	Timepoint(s) of evaluation of this outcome measure (if applicable)
Primary Objective To compare results of [A] ploidy and [B] stroma analysis with outcome after surgery to remove early rectal cancer	Correlation between [A] ploidy status and [B] tumour: stroma ratio with local recurrence of cancer	Time between surgery for rectal cancer and local recurrence
Secondary Objectives To compare results of ploidy and stroma analysis with survival after surgery to remove early rectal cancer To assess predictive value of [A] ploidy and [B] stroma analysis for outcome after surgery to remove early rectal cancer To compare results of [A] ploidy and [B] stroma analysis with outcomes by use of adjuvant treatment	Correlation between [A] ploidy and [B] stroma analysis with overall survival after TEM surgery to remove rectal cancer Contribution of [A] ploidy and [B] stroma analysis to a regression model for local recurrence after TEM surgery to remove rectal cancer Subgroup analysis comparing [A] ploidy and [B] stroma results with local recurrence and survival for patients who did and did not receive adjuvant chemo- or radiotherapy	Time between surgery for rectal cancer and death

6. STUDY DESIGN

An observational study to correlate the results of ploidy and stroma analysis with prognosis in early rectal cancer

IRAS reference: 195159 REC reference: 16/WM/0443

CONFIDENTIAL

Date and version No: 21 October 2016 v1.1

Page 6 of 16

This is an observational study comparing results of two specialised pathology tests with outcome after surgical removal of early rectal cancer. No extra interventions will be carried out on patients.

Over 170 patients have already had an early rectal cancer removed by minimally-invasive surgery (transanal endoscopic microsurgery or TEM) since 2007 in Oxford, and more operations take place each month. Data about the tumour and follow-up on these patients is routinely collected in the Oxford TEM database to ensure that patients receive the appropriate investigations and management after surgery, and that any recurrence of the tumour is promptly detected and treated.

For patients who agree to take part in this study, or who consented to donation of tissue for research at the time of surgery, we will perform the extra pathology tests on the tissue which is stored in the Oxford pathology department as standard practice, and compare the test results with the outcome information contained in the TEM database.

The extra pathology tests will be undertaken in a specialist department in Oslo, Norway. The study will involve sending a small section of the preserved tissue from each consenting patient to Norway for analysis. After analysis, any residual parts of the samples will be returned to the Oxford pathology department.

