8. STUDY PROCEDURES

8.1. Recruitment

All patients who have undergone TEM surgery to remove a rectal cancer since 2007 are eligible, as well as new patients having surgery over the study period. Data on these patients is recorded as standard practice in the Oxford TEM database. There will be different groups, according to the time of surgery and whether or not potential participants consented for tissue donation, requiring different identification and recruitment strategies.

Already had surgery groups

Screening: A member of the care team will extract a list of patients who have had TEM surgery for rectal cancer since 2007 from the TEM database, identified by MRN (OUH medical records number) only. The care team member will then screen the casenotes for these patients to determine whether or not they consented to donation of tissue for research on the surgical consent form.

- Group A: Those who already consented for tissue donation

The majority of potential participants signed a donation of tissue for research statement at the time of surgery. If this statement has been agreed to, patients will be considered to have consented to participate in the study. The care team member will pass the list of MRNs (and linked anonymized data) for these patients to the researcher.

- Groups B & C: Those who did not consent to tissue donation at the time of surgery

Once these have been identified, the care team member will identify whether these patients are still undergoing follow-up at Oxford hospitals. For those who are undergoing follow-up (Group B) the member of the care team will provide the researcher with the MRN and date of the next follow-up appointment. For those who are no longer under follow-up (Group C), the member of the care team will post an information sheet and consent form to the potential participant.

For Group B the researcher will contact the patient during their follow-up visit and give them an information sheet about the study. They will be invited to sign a consent form if they wish to participate. Group C will receive an information sheet and consent form through the post, and will be provided with a telephone number should they wish to discuss the study further.

New patients who have not yet had surgery (Group D)

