8.5. Data Handling

For Group A patients, who gave consent at the time of surgery, a member of the care team will extract the relevant data, including tumour characteristics, any (neo-)adjuvant treatment details and outcome information, identified only by MRN, from the TEM database. The care team member will then securely transfer this anonymised data, identifiable by MRN only, to the research team. The research team will then allocate each participant a study ID according to the recruitment log, and replace the MRN with the unique study ID. The transfer will be done using a password protected spreadsheet sent via encrypted email. For all other patients, who sign a specific study consent form, the researcher will prepare the data extract from the TEM database, identified only by MRN, and then replace the MRN with a study ID. The researcher will securely provide a list of MRNs, with date of surgery, to the pathology department. The MRNs will be linked to a unique study ID in a separate recruitment log.

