10.3. Data Recording and Record Keeping

For Group A patients who consented at the time of surgery, a member of the care team will prepare a data extract for all participants from the TEM database, in the form of an Excel spreadsheet, and securely transfer this anonymised data, identifiable by MRN only, to the research team. The research team will then allocate each participant a study ID according to the recruitment log, and replace the MRN with the unique study ID. For all other patients, who sign a specific study consent form, the researcher will prepare the data extract from the TEM database, identified only by MRN, and then replace the MRN with a study ID. All subsequent study data will be entered into the Excel spreadsheet. Data from this study will be generated at the Oxford University Hospitals and Institute for Cancer Genetics and Informatics, Oslo. Data will be analysed at the Oxford University Hospitals by the research investigators. Personal data will be stored and accessed by the investigators for less than 3 months. Research data will be stored for 10 years after the completion of the study.

The participants will be identified by a unique study specific number in the study database. For those who previously consented for tissue donation the MRN will be linked to the unique study number in the recruitment log. All other participants who consent will also be assigned a unique study identifier linked to their personal information. The name and any other identifying detail will NOT be included in any study data electronic file.

All electronic data will be password-protected and anonymised. All hard copy files and data will be kept in a locked cabinet within a locked office with restricted access. Access to the data will be restricted to study team members. The NHS Code of Confidentiality will be followed. This study will follow the sponsor organisation's policy regarding data storage and the NHS Code of Confidentiality. Information derived from the study will be stored on a single, secure (password encryption) NHS computer. This will be positioned within a secure location in the hospital.

Participants will be informed using patient information sheets of how data will be stored (only participants who did not sign a tissue donation form at the time of surgery will receive patient information sheets). The principal investigators will constantly review the security of research data files.

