12.7. Other Ethical Considerations

The majority of potential patients will have consented to tissue donation and anonymous use, and use of anonymous data for research at the time of surgery. In order to link the tissue and data, the tissue must be made identifiable. It is not feasible to contact this participant group for consent to link the data and tissue; as the surgical procedures date back to 2007, many potential participants may have moved from the Oxford area and some may be deceased. The data and sample will be linked using the hospital MRN number. This is a trust-specific reference number outside the OUHFT participants are not identifiable by this number. Once linked the data and samples will also be re-anonymised (or linked anonymised). There will be no onward disclosure of patient data outside the care team, as the researcher is also part of the participants' care team.

Tissue samples will be transferred outside the UK. A material transfer agreement will be in place to cover the terms of the transfer of the samples to the Institute of Cancer Genetics and Informatics in Oslo. The samples will be identifiable by study ID only, when they are transferred to Norway. Participants consent to the transfer of their linked anonymised samples to Norway.

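### The TEM database is the only outcome source named, so events after a patient's last Oxford contact may be missed, and the stated 18-month minimum follow-up is not secured

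*Combined protocol and SAP*

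**What the plan says.** Section 6 describes the database as a routine clinical record ("Data about the tumour and follow-up on these patients is routinely collected in the Oxford TEM database") and says the study will "compare the test results with the outcome information contained in the TEM database". Both extraction routes draw on it. For Group A (past patients who agreed to tissue donation at surgery), section 8.5 has the care team "extract the relevant data, including tumour characteristics, any (neo-)adjuvant treatment details and outcome information, identified only by MRN, from the TEM database". For everyone else, section 10.3 says "the researcher will prepare the data extract from the TEM database, identified only by MRN, and then replace the MRN with a study ID". Section 10.1 lists hospital records and correspondence among source documents, but generically, and ties none of them to recurrence or death.

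Two parts of the cohort may lie outside Oxford's view. Section 8.1 says "For those who are no longer under follow-up (Group C), the member of the care team will post an information sheet and consent form". Section 12.7 says of the tissue-donation patients, whom 8.1 calls the majority, that "many potential participants may have moved from the Oxford area and some may be deceased". It gives this as the reason for not contacting them.

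The synopsis gives follow-up as "Minimum 18 months" and a study period of 2 years; section 9.2 expects recruitment to take 18 months. Section 5 defines the endpoints as times from surgery to local recurrence and to death. Sections 9.1 to 9.6 give no censoring rule, data cut-off or approach to loss to follow-up. Section 9.5 rules out imputation, and 9.6 includes everyone who consents.

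**The concern.** Local recurrence is the primary endpoint and overall survival the first secondary one. Both depend on knowing how long each patient was actually observed. A recurrence treated elsewhere does not show up as a blank cell. It looks the same as no recurrence, so the missing-data rule in 9.5 would not detect it. The protocol recognises that patients may have moved or died, but only as a consent problem; it does not carry this through to outcomes.

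Three things are at stake. Events are lost from a study of 150 patients with no stated event rate. Recurrence and survival figures may be too favourable. And if leaving Oxford is related to marker status or to outcome, the marker association itself may be distorted. The follow-up stated in the synopsis would also describe something the design does not guarantee.

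**Working it through.** **1. The plan's own follow-up figure.** The study period is 24 months (synopsis) and recruitment takes 18 months (9.2). A new patient operated on at the end of recruitment has at most 24 − 18 = 6 months by the planned end, against the stated 18. No criterion in 7.2 or 7.3 requires a length of follow-up. Section 8.8 ends the study on receipt of the last laboratory result, which is unrelated to follow-up. A past patient last seen 6 months after surgery is eligible and is analysed.

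**2. What can be checked of the 150.** Nothing: 9.2 gives no power, effect size, event rate or dropout. All that follows is illustration on assumed inputs.

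**3. Events unseen in a leaver, if counted as event-free.** Assume a constant hazard giving 15% local recurrence at 36 months: h = −ln(0.85)/3 = 0.0542 per year.

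- Last seen at 24 months, read at 72: true risk 1 − exp(−6h) = 27.8%; recorded 1 − exp(−2h) = 10.3%; share missed (27.8 − 10.3)/27.8 = 63%.
- Last seen at 60 months, read at 72: about 14% missed.
- Last seen at 24 months, read at 36 (the horizon mentioned in section 4): (15 − 10.3)/15, about 32% missed.

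In the first case the whole-cohort figure is 27.8 − share × 17.5. With 10%, 25% or 40% leavers it falls from 27.8% to 26.0%, 23.4% or 20.8%.

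The same sum for survival, with assumed mortality of 0.04 per year, last contact at 3 years and reading at 8: truth is exp(−0.32) = 73%, and leavers appear as exp(−0.12) = 89%. The cohort figure becomes 74%, 77% or 79%.

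**4. Loss of precision, whatever the censoring rule.** Let f be the share who leave and m the share of their events unseen. Events = 150 × risk × (1 − f × m). Power is by Schoenfeld's formula, two-sided 0.05, 50:50 marker split, hazard ratio 2.5.

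| True recurrence | All events seen: events, power | f = 0.2, m = 0.5 | f = 0.4, m = 1 |
|---|---|---|---|
| 10% | 15, 43% | 13.5, 39% | 9, 28% |
| 15% | 22.5, 58% | 20.2, 54% | 13.5, 39% |
| 20% | 30, 71% | 27, 66% | 18, 49% |
| 30% | 45, 87% | 40.5, 83% | 27, 66% |

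**5. Bias depends on the unstated rule.** Simulation of 400,000 patients: death hazards 0.06 and 0.03 per year by marker (true hazard ratio 2), potential follow-up 1.5 to 11 years, leavers last seen at 0.5 to 5 years. The hazard ratio is estimated as the ratio of event rates per person-year; true 5-year survival is about 80%.

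| Who leaves | Censored at last contact: 5-year survival, HR | Event-free to extract: 5-year survival, HR |
|---|---|---|
| 20% in both marker groups | 80.0%, 1.97 | 81.7%, 1.96 |
| 40% in both marker groups | 79.9%, 2.00 | 83.4%, 2.00 |
| 40% marker-positive, 20% marker-negative | 80.4%, 2.00 | 82.9%, 1.73 |

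In these simulations leaving is unrelated to outcome within each marker group. Censoring at last contact then recovers survival and hazard ratio. Counting leavers as event-free inflates survival by about 2 to 3 points, and moves the hazard ratio only when leaving differs by marker.

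**The case against.** The strongest reply is that the documents do not establish that anything is missed. They do not say how the database is updated, and news from other hospitals may reach it. The endpoints are defined as times, which fits censoring at last contact, and step 5 shows that this removes most of the bias if leaving is uninformative. The illustrations use leaver shares and event rates that appear nowhere in the protocol, and the size of the effect moves widely with them. All of this stands, and it is why the point is put conditionally. It does not close the gap: no rule commits the analysis to censoring at last contact, no last-contact date is listed for extraction, and censoring cannot restore lost events.

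A reader might infer three stronger things that the documents do not support.

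- That events elsewhere cannot come back because the hospital number identifies nobody outside the trust. Section 12.7 says this about confidentiality; it says nothing about how clinical news reaches the database.
- That Group C is under-recorded by its very definition. If recurrence tends to keep patients at Oxford, Group C is selected for patients without recurrence up to the time they left. That is selection, not under-recording.
- That deaths are missed in Group C before consent. Its members must sign and return a form (8.3), so they are alive at that point. Missed deaths concern mainly Group A, and any group after last contact.

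**Conclusion.** The point holds in conditional form. One outcome source is named, part of the cohort is or may be beyond its reach, and nothing in the plan records how long each patient was truly observed. Events after last Oxford contact may be missed, and those patients may be counted as event-free if recurrence is treated as yes/no or time is run to the extract date. It would go too far to say that they will be.

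The firmest consequence of any missed events is fewer events: a 10% loss at f = 0.2, m = 0.5 and a 40% loss at f = 0.4, m = 1. Over-favourable rates follow only under the event-free reading. Bias in the marker association needs leaving to be related to marker status or to outcome, and the documents give no evidence on either. All these sizes rest on assumed inputs.

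The follow-up shortfall needs no such assumption: it follows from the protocol's own 18 and 24 months and from the absence of any follow-up requirement.

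**What to change.** 1. In the casenote screen that 8.1 already plans for past patients, Group A included, record the date last assessed for recurrence, vital status and the date last known alive. Extract the same items for Groups B and D.
2. Add a recurrence question and permission to contact the GP to the Group C form. That mailing does not reach Group A, so seek vital status for Group A where existing approvals allow. The casenotes alone will mostly give Group A dates for censoring rather than outcomes recorded elsewhere.
3. State that recurrence is censored at the last documented assessment and survival at the date last known alive. Report completeness of follow-up by marker status and by recruitment group.
4. Restate the 18-month minimum as the follow-up actually achieved, or set the data cut-off so that it is met. For a new patient operated on at month 18, that means month 18 + 18 = 36, a year past the planned end. A later cut-off would not by itself lengthen documented follow-up for past patients who left early.

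The cost is a few extra columns in a screen already being done and a small amendment to the Group C form. Stated follow-up will be shorter for some patients.
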